#### 4. Open-label Passive follow-up phase

With Amendment 7, the active follow-up of new suspected COVID-19 is replaced by a passive follow-up. Participants will enter this phase on the day of consenting to Amendment 7 (or with the stop of the eCOA at each study site, which ever date comes first) until end of study.

In the passive follow-up phase, the same cohorts as from the booster phase are included, and all data will be descriptively presented by cohort depending on the vaccination schedule received during the follow-up. Since COVID-19 reporting changed from an active approach to a passive approach, the effectiveness evaluations may be limited and will be described in the SAP as applicable.

The secondary and exploratory objectives and endpoints for the passive follow-up phase of the study are:

Objectives	Endpoints
The secondary safety objective of the double-blind phase (see double-blind objectives).	
 
The secondary safety endpoint of the double-blind phase (see double-blind endpoints).
 

To evaluate COVID-19 in terms of (S)AEs MAAEs, hospitalizations and fatal AEs linked to COVID-19*	
 
SAEs and AEs linked to COVID-19.
 
MAAEs linked to COVID-19
 
SAEs linked to COVID-19 that require hospitalization
 
Fatal AEs linked to COVID-19
 

In the immunogenicity subset of participants: to evaluate the immunogenicity of Ad26.COV2.S at available timepoints	
 
Analysis of antibodies binding to the SARS-CoV-2 S protein by ELISA
 

Objectives	Endpoints
In the Heterologous and Homologous Booster Subsets: to compare the immune responses 28 days following booster dose administration	
 
Analysis of antibodies binding to the SARS-CoV-2 S protein by ELISA
 
Qualitative comparison of responses in terms of binding, neutralizing antibody against Wuhan reference strain and variants of interest utilizing wtVNA and/or psVNA, depending on feasibility
 

\* Refer to Section 8.3 for the safety follow up and COVID 19 reporting requirements as of Protocol Amendment 7.

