Up to Amendment 7, any positive RT-PCR test result regardless if it is obtained outside the study or at a study visit will be considered a trigger to start COVID-19 procedures. All participants with COVID-19-like signs or symptoms meeting the prespecified criteria for suspected COVID-19 and all participants with at least 1 positive RT-PCR test for SARS-CoV-2 on COVID-19 Day 1-2 or Day 3-5 visits, should undertake the COVID-19 procedures until 14 days after symptom onset (COVID-19 Day 15) or until resolution of the COVID-19 episode, whichever comes last. However, participants with COVID-19-like signs or symptoms meeting the prespecified criteria for suspected COVID-19 should stop the COVID-19 procedures as soon as it is confirmed that both nasal swabs collected on COVID-19 Day 1-2 and Day 3-5 are negative for SARS-CoV-2. Resolution of the COVID-19 episode is defined as having 2 consecutive SARS-CoV-2

negative nasal swabs and 2 consecutive days with no COVID-19-related signs or symptoms. At the time of resolution of the COVID-19 episode, the collected information will be applied against the clinical case definition. As from Amendment 7, this active follow-up approach will no longer be pursued and will be replaced by passive follow-up. Passive follow-up of COVID-19 consists of recording of new COVID-19 episodes as SAEs, AEs, or MAAEs. The information of these AEs is collected during the scheduled phone calls with the participants. Positive COVID-19 laboratory findings should be reported in the eCRF, if available (eg, positive PCR results, positive nasal swab).

All necessary precautions (as per local regulation) should be taken to protect medical staff and other contacts of participants who are suspected to have COVID-19 until proven negative by molecular techniques or who are positive AND meet the prespecified criteria for suspected COVID-19 on COVID-19 Day 1-2 and Day 3-5 until they are no longer positive. In the event of a confirmed SARS-CoV-2 infection, the participant and participant's medical care provider will be notified, and the participant will be asked to adhere to the appropriate measures and restrictions as defined by local regulations.

A DSMB will be commissioned for this study.

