## SAFETY EVALUATIONS

The first 2,000 participants in each of the 2 age groups will remain under observation at the study site for at least 30 minutes post-vaccination to monitor for the development of acute reactions. If at the time of the Day 3 safety review of the initial 2,000 participants no acute reactions have been observed in the age groups, the observation period at the study site may be reduced to at least 15 minutes post-vaccination for the remaining participants in the study.

For all participants (throughout the study regardless of any protocol amendment):

- (S)AEs that are related to study procedures or that are related to non-investigational sponsor products will be reported from the time a signed and dated informed consent form (ICF) is obtained until the end of the study/early withdrawal.
- Clinically relevant medical events not meeting the above criteria and occurring between signing of the ICF and moment of vaccination in the double-blind phase of the study will be collected on the Medical History electronic case report form (eCRF) page as pre-existing conditions. This does not apply to the open-label phase.
- All SAEs and all AEs leading to study discontinuation (regardless of the causal relationship) are to be reported from the moment of vaccination until completion of the participant's last study-related procedure, which may include contact for safety follow-up. The sponsor will evaluate any safety information that is spontaneously reported by an investigator beyond the time frame specified in the protocol.
- MAAEs are defined as AEs with medically-attended visits including hospital, emergency room, urgent care clinic, or other visits to or from medical personnel for any reason. Routine study visits will not be considered medically-attended visits. New onset of chronic diseases will be collected as part of the MAAEs. MAAEs are to be reported for all participants from the moment of each vaccination until 6 months after the vaccination (applicable for both the double-blind and open-label phases of the study), except for MAAEs leading to study discontinuation which are to be reported during the entire study.
- Special reporting situations, whether serious or non-serious, will be recorded from the time of each vaccination until 28 days post-vaccination (applicable for both the double-blind and open-label phases of the study).

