- Suspected AESIs (thrombotic events and thrombocytopenia [defined as platelet count below 150,000/ $\mu$ Lb]) will be reported from the moment of vaccination until the end of the study/early

a Vaccination with Ad26.COV2.S may interfere with some serologic assays utilized at local community health clinics/commercial laboratories, by seeking and identifying the spike protein in the vaccine and rendering a false positive result. For this reason, participants will be encouraged to not seek testing outside the study. If a participant requires testing outside of the protocol-mandated testing schedule, the site will guide them on the appropriate assay that identifies the viral nucleocapsid protein (and not the spike protein).

b Updated Proposed Brighton Collaboration process for developing a standard case definition for study of new clinical syndrome X, as applied to Thrombosis with Thrombocytopenia Syndrome (TTS). 18 May 2021. <https://brightoncollaboration.us/wp-content/uploads/2021/05/TTS-Interim-Case-Definition-v10.16.3-May-23-2021.pdf>. Accessed: 02 September 2021.

withdrawal. An AESI Adjudication Committee with appropriate expertise will be established to evaluate each suspected AESI and determine whether it is a case of thrombosis with thrombocytopenia syndrome (TTS). From the time of local approval of protocol Amendment 5 onwards, TTS is considered an adverse event of special interest (AESI).

- All AEs will be followed until resolution or until clinically stable.

As of Amendment 7, for all participants:

- Active follow-up of suspected COVID-19 episodes will be replaced by passive surveillance: during follow-up calls by the site at Month 18 and Month 24, new COVID-19 participant-reported events are to be reported as SAEs, AE or MAAEs.
- Concomitant medications for these events should be reported.
- If a COVID-19 confirmatory laboratory or assay read-out is available, this should be reported in the eCRF (self-reported or as part of CIOMS form).

For participants in the Safety Subset (double-blind phase):

- Solicited AEs, collected through an e-Diary, will be recorded from the time of vaccination until 7 days post-vaccination.
- All other unsolicited AEs, whether serious or non-serious, will be recorded from the time of vaccination until 28 days post-vaccination.

Up to Amendment 7: For participants who received booster vaccination at the Year 1/Booster Visit:

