- f. Investigator must check for acute illness or body temperature  $\geq 38.0^{\circ}\text{C}/100.4^{\circ}\text{F}$  at the time of each vaccination. If any of these events occur at the scheduled time for the booster vaccination, the Year 1/Booster Visit with active vaccine can be delayed within the preferred visit window.
- g. MAAEs are to be reported for all participants from the moment of each vaccination until 6 months after the booster vaccination, except for MAAEs leading to study discontinuation which are to be reported during the entire study. New onset of chronic diseases will be collected as part of the MAAEs.
- h. All (S)AEs related to study procedures or non-investigational sponsor products will be reported from the time a signed and dated ICF is obtained until the end of the study/early withdrawal. All other SAEs are to be reported from the moment of vaccination until completion of the participant's last study-related procedure. AEs leading to study discontinuation (regardless of the causal relationship) and AESIs are to be reported from the moment of vaccination until completion of the participant's last study-related procedure. Suspected AESIs are to be reported from the moment of vaccination until completion of the participant's last study-related procedure (see Section 8.3.1). Special reporting situations, whether serious or non-serious, are to be recorded from the time of booster vaccination until 28 days post-vaccination.
- i. From the moment the ICF for Amendment 7 is signed, the participant moves to the passive follow-up phase schedule. COVID-19 is to be reported as SAE, AE, or MAAE until study end (see Section 8.3.1 for the reporting of COVID-19 events as of protocol amendment 7). Ongoing COVID 19 episodes from the date of Amendment 7 approval will not be reported as SAEs, AEs, or MAAEs. Participants may contact the site at any time in between scheduled visits to report COVID-19 episodes.
- j. Refer to Section 6.10 for collection and recording of concomitant therapies associated with SAEs, solicited and unsolicited AEs, suspected AESIs, and MAAEs and COVID-19 (S)AEs or COVID-19 MAAEs.

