- l. From the moment the ICF for Amendment 7 is signed, the participant moves to the passive surveillance phase schedule. COVID-19 is to be reported as SAE, AE, or MAAE until study end (see Section 8.3.1 for the reporting of COVID-19 events as of protocol amendment 7). Participants may contact the site at any time in between scheduled visits to report COVID-19 episodes.

- m. Refer to Section 6.10 for collection and recording of concomitant therapies associated with SAEs, solicited and unsolicited AEs, suspected AESIs, and MAAEs and new COVID-19 (S)AEs or COVID-19 MAAEs.
- n. Whole blood samples will be used for a complete blood count, including platelets, in a local laboratory or a substitute for local laboratory, depending on local feasibility towards turnaround time of sample processing. Serum samples will be derived from the whole blood sample and stored for potential future coagulation-related testing in a central laboratory if the participant experiences a suspected AESI (see Section 10.2, Appendix 2).
- o. Blood samples for immunogenicity will only be taken if the early exit visit is at least 10 days after the previous immunogenicity blood draw.
- p. Blood sample for humoral immunity at Year 1/Booster Visit (prior to booster vaccination), Month 18, and Year 2, and additionally 28 days and 72 days after booster vaccination, if applicable, may also include sample for sero-confirmation of SARS-CoV-2 infection. Samples will be collected for 400 participants at selected sites.
- q. Blood sample for humoral immunity at the Year 1/Booster Visit (pre-vaccination) and 28 days, 72 days, 6 months, and 1 year after booster vaccination, may also include sample for sero-confirmation of SARS-CoV-2 infection. Samples will be collected for 600 participants at selected sites.
- r. The approximate blood volume collected depends on which one of the immunogenicity or booster subgroups the participant is in.
- s. No further booster doses will be administered under protocol amendment 7, except if there was a medical reason that prevented a participant to receive the Ad26COV2.S vaccine prior to acceptance of amendment 7 or if there is a non-availability of other vaccines to the participant. The investigator should inform participants on the availability of other COVID-19 vaccines.

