### 1.3.4. Participants With (Suspected) COVID-19

#### 1.3.4.1. Passive Follow-up (As of Amendment 7)

As of Amendment 7, active follow-up of suspected COVID-19 episodes will be replaced by a passive follow-up approach.

New suspected COVID-19 episodes will be participant-reported and will not include any laboratory sampling. Site staff will collect information on the new COVID-19 episodes at scheduled time points and report these as SAEs, AEs, or MAAEs, as applicable. Participants may contact the site at any time in between scheduled visits to report COVID-19 episodes. Concomitant therapies related to these events are to be reported, as well as any confirmatory COVID-19 laboratory information, if available.

Guidance on (S)AE coding may be provided.

Some participants will have an ongoing COVID-19 event at time of signing the informed consent of protocol amendment 7. Also, under protocol amendment 7, the eCOA will be decommissioned. Hence participant will stop using the eCOA as of the consent visit. The outstanding activities planned for the follow-up of COVID-19 events will also end on that date for the participants (eg no further samples, no MRU completion, no MA-COV completion, no further visit in the context of the COVID-19 follow-up). The eCOA will be stopped based on approval of protocol Amendment 7 at each study site.

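### Amendment 7 hand-over: the footnote barring reports of ongoing COVID-19 episodes contradicts the general SAE rule, and the hand-over date is set in three different ways

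*Protocol*

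**What the plan says.** Section 1.3.4.1 recognises that the switch will catch some people mid-illness: "Some participants will have an ongoing COVID-19 event at time of signing the informed consent of protocol amendment 7". For them, "The outstanding activities planned for the follow-up of COVID-19 events will also end on that date for the participants". That covers samples, the medical resource and medically-attended COVID-19 forms, and COVID-19 visits.

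What takes over is limited to new episodes. The Synopsis (Overall Design) says: "Passive follow-up of COVID-19 consists of recording of new COVID-19 episodes as SAEs, AEs, or MAAEs". The Synopsis (Safety Evaluations) says that "new COVID-19 participant-reported events are to be reported as SAEs, AE or MAAEs".

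Footnote i of Section 1.3.1 then adds: "Ongoing COVID 19 episodes from the date of Amendment 7 approval will not be reported as SAEs, AEs, or MAAEs". The corresponding footnote l of Section 1.3.2, for the Immunogenicity and Booster Subsets, has no such sentence.

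The general safety rules in the Synopsis are declared to hold for all participants whatever amendment is in force. They include: "All SAEs and all AEs leading to study discontinuation (regardless of the causal relationship) are to be reported from the moment of vaccination". Footnote h of Section 1.3.1 repeats the SAE duty up to the last study procedure, with no exception for COVID-19. Section 2.1 states that Amendment 7 leaves safety follow-up unchanged.

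On timing, the Synopsis (Open-label Passive follow-up phase) says: "Participants will enter this phase on the day of consenting to Amendment 7 (or with the stop of the eCOA at each study site", taking the earlier of the two. Footnote l of Section 1.3.2 says: "From the moment the ICF for Amendment 7 is signed, the participant moves to the passive surveillance phase schedule", and footnote i of Section 1.3.1 says much the same.

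**The concern.** An episode in progress at the switch loses its active procedures and is not new, so it does not clearly enter passive follow-up. Footnote i then tells the site not to report it through the safety system. If that participant is later admitted to hospital or dies of the episode, a site working from its schedule of activities has an explicit instruction not to file what the general rules require it to file.

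Two things are at stake. One is completeness of serious event reporting. The other is the open-label severity data: severe/critical disease and COVID-19 death in the cross-over phase, hospitalisation and death in the booster phase, and the ratio of long COVID-19 cases (lasting more than 28 days) in both. Long episodes are the likeliest to straddle a fixed date.

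**Working it through.** The protocol gives no figure to reproduce here, so the check sets its rules side by side.

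**Is a serious event after hand-over, in an ongoing episode, reportable?**

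- Section 1.3.1 footnote i: no; SAEs are named expressly.
- Section 1.3.1 footnote h: yes; all other SAEs to the last study procedure.
- Synopsis, Safety Evaluations: yes; all participants, under any amendment. AEs are followed to resolution or stability.
- Section 2.1: safety follow-up is unchanged.
- Section 1.3.2 footnote l: the exclusion is absent.
- Section 4.1: confirmed COVID-19 and its complications go into the eCRF for the whole study, yet another paragraph of the same section monitors complications only up to Amendment 7.

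Footnotes h and i cannot both be obeyed for such an event. Footnote i is the more specific.

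**Which date governs?**

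1. The exclusion in footnote i runs from Amendment 7 approval.
2. The passive schedule starts at signature of the consent form (Section 1.3.1 footnote i, Section 1.3.2 footnote l).
3. The passive phase starts at consent or eCOA stop, whichever is first (Synopsis, Section 3.3).

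Section 1.3.4.1 itself ties the eCOA stop both to the consent visit and to site approval. Section 1.3 asks for re-consent preferably within 4 weeks (28 days) of approval and sets no upper limit. Taking episodes by onset:

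- Onset before approval, still ongoing: excluded from reporting at approval, although Section 1.3.4.1 continues active procedures until consent.
- Onset between approval and consent, ongoing at consent: in the passive phase if the eCOA has stopped, but under the active schedule by the consent-based rule. Whether footnote i counts it as ongoing is unclear.
- Onset after consent: passive under every rule.

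The first two groups depend on which sentence a site or programmer follows.

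**How is a truncated episode classified?**

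The Synopsis applies the case definition at resolution, defined as two negative swabs in succession plus two symptom-free days in succession. Study sampling ends at hand-over, so an unresolved episode can no longer meet that definition from study swabs. After Amendment 7 the severity committee may work from AE/SAE data, CIOMS forms and local laboratory results; footnote i removes the AE/SAE source for these episodes. No rule in the text available says how they are then classified.

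For the long-COVID ratio, an episode starting d days before the stop has at most d days of active observation. A duration above 28 days can be seen only if d > 28. With d ≤ 28 and no recorded end date, the episode is neither long nor short.

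**The case against.** A reader might infer that events in ongoing episodes simply cannot be reported. The text does not establish that. Footnote h and the Synopsis still require SAE reporting, and the Synopsis (Efficacy Evaluations) has COVID-19 hospitalisation and death monitored throughout. The sentence may be meant only to stop an episode already in the active dataset from being entered again as a new AE. Footnote i also refers to Section 8.3.1, which was not available for this check and may settle the matter. All of this stands. It makes the defect a contradiction with possible loss, not a certain gap, but footnote i as worded would still conflict with the Synopsis.

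A reader might also infer that new episodes between eCOA stop and consent go uncollected. That is not supported. The phase definition places them in passive follow-up, and the Month 18 and Month 24 calls collect new events for all participants, with no stated limit to events after signature. What remains is inconsistent start dates.

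The contrast between subset and other participants should not be overdrawn: passive follow-up is confined to new episodes for both, and only the explicit bar differs.

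Severity reached before hand-over is kept, because the criteria may be met at any time during observation, and readjudication is allowed when new information arrives. The booster-phase analyses are declared descriptive, open-label efficacy is evaluated only if feasible, and Section 2.1 acknowledges the limits of open-label efficacy data.

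**Conclusion.** The point holds as a contradiction in the reporting rules. A site that follows footnote i of Section 1.3.1 could omit a hospitalisation or death occurring after hand-over in an ongoing episode, which other parts of the protocol require it to report. The truncated episodes also have no stated classification in the open-label severity, death and long-COVID endpoints, and the hand-over date is inconsistent.

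The size cannot be calculated. The protocol gives neither the number of participants under follow-up at the switch, nor the incidence at that time, nor the number of ongoing episodes. A count built on assumed inputs would also mix mostly non-serious episodes with the few that matter. The only relevant figures are the 28-day preferred interval from approval to re-consent, without an upper limit, and the 28-day long-COVID threshold.

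The double-blind analysis is complete according to Section 2.1 and is not exposed. The conclusion rests on the sections available and should be checked against Section 8.3.1.

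**What to change.** 1. Delete the footnote i sentence, or limit it: an episode already in the active dataset is not re-entered as a new AE, but any event meeting SAE criteria, or MAAE criteria within the MAAE reporting window, after hand-over is reported.
2. Use the same footnote in Sections 1.3.1 and 1.3.2, and check it against Section 8.3.1.
3. Define one hand-over date and use it in the schedules, Section 1.3.4.1 and the phase definitions. At the consent contact, ask about new episodes since eCOA stop.
4. For each episode ongoing at hand-over, record end date, hospitalisation, ICU admission and death at the next scheduled contact, and assign the episode to the active phase by onset date.
5. Treat an episode with 28 days or less of observation before the stop and no recorded end date as not evaluable for the long-COVID ratio.

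The cost is a protocol clarification and a few questions at contacts already planned. No new visits or samples are needed.
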